9.4.3 Subject Numbering

Each subject will be assigned a unique 6-digit subject number by the study staff. The subject number will consist of a 3-digit clinical investigational site number assigned by the Sponsor, followed by a three-digit subject number (e.g., 001) assigned by the study staff.

The clinical site is responsible for maintaining a current log of subject number assignments and bottle numbers of the investigational product administered to each subject. The subject's initials (first/middle/last) and unique subject number are required to be entered on all clinical investigation documentation (i.e., CRFs, labeling of clinical materials and samples containers, drug accountability logs, etc.)

9.4.4 Study Dosing and Dosage Adjustments For subjects >30 kg

After Sponsor and Principal Investigator have reviewed subject's history, baseline seizure data and inclusion/exclusion criteria and determined a subject to be eligible for the study, ganaxolone treatment will be initiated at a dose of 900 mg/day in divided doses. The dose will be increased by approximately 20 to 50% (e.g., an increase from 900 mg/day to 1200 mg/day is a 33% increase) at intervals of not less than 3 days and not more than 2 weeks provided current dose is reasonably tolerated, until desired efficacy is achieved or a maximally tolerated dose (MTD) level is reached. Subsequent dose adjustments should

be made in increments of approximately 20 to 50% with a minimum of three days between dose changes, unless required for safety. Any and each dose escalation above 1500 mg/day requires a clinic visit scheduled 4-6 days after the dose increase to assess safety and tolerability. The maximum allowable dose is 1800 mg/day.

For subjects ≤30 kg

For children weighing 30 kg (66 lbs) or less, dosing should start at 18 mg/kg/day and be increased in ~20-50% increments at intervals of not less than 3 days and not more than 2 weeks provided current dose is reasonably tolerated, until desired efficacy is achieved or a maximally tolerated dose (MTD) level is reached. Subsequent dose adjustments should be made in increments of ~20-50% with a minimum of three days between dose changes, unless required for safety. Any and each dose escalation above 54 mg/kg/day requires a clinic visit scheduled 4-6 days after the dose increase to assess safety and tolerability. The maximum allowable dose is 63 mg/kg/day. (see Appendix 4 for suggested dose escalation schedule.)

DOWN TITRATION

At the conclusion of the study, or upon discontinuation if the subject is terminated from the study prior to Week 26, a period of down-titration from 1 to 4 weeks should be initiated. The down-titration duration will be determined by the site investigator with input from the Sponsor based on subject's age, weight, dose and duration on study medication.

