9.5.4 Other Assessments

Blood samples will be drawn at baseline, 2 weeks, 8 weeks, 26 weeks, all visits in the 52 week extension and at unscheduled visits as needed for evaluation of blood chemistry and hematology, and/or to measure levels of ganaxolone, concomitant AED medications, allopregnanolone, and related endogenous CNS-active steroids. (See Appendix 2 Schedule of Events).

EEG will be collected at baseline and at visit 4, 5, 6 and 7 and at all visits in the 52 week extension.

The Visual Analogue Scale (VAS-Targeted Behavior) will be collected at baseline and at Visits 5, 7, 9 and 10.

The time of the blood sample collection, and the time of the most recent dose prior to the blood sample collection will be recorded. Samples of blood will be centrifuged to obtained plasma, which will be stored frozen (-20°C) until analysis.

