9.5.5.2 Visit 2 (Baseline; Week 0)

- Review medical history, background AEDs and other concomitant medications
- Review inclusion/exclusion criteria
- Collect and review seizure calendars
- VAS
- Administer Columbia Suicide Scale assessed for children 7 years and older
- Perform physical and neurological examinations
- Measure vital signs
- Draw blood sample for, hematology, chemistry, trough concomitant AED levels, and allopregnanolone, and related endogenous CNS-active steroids; obtain urine sample from subjects who are toilet trained for urinalysis and pregnancy test for WCBP.
- Dispense study medication and dosing instructions
- Instruct and provide study Subject Seizure Calendar
- EEG

- Screening and Baseline visits may be one visit if the seizure calendar data are sufficient.
- 9.5.5.3 Visit 3 (end of Week 2 + / 3 days)
 - Review background AEDs and other concomitant medications
 - Collect and review seizure calendars; provide new calendars
 - Administer Columbia Suicide Scale assessed for children 7 years and older
 - Perform follow-up physical and neurological examinations
 - Assess for adverse events
 - Measure vital signs
 - Collect bottles from prior visit study medication
 - Adjust dose if necessary
 - Dispense study medication
- 9.5.5.4 Visit 4 (end of Week 4 +/- 3 days)
 - Review background AEDs and other concomitant medications
 - Collect and review seizure calendars; provide new calendars
 - Complete CGII-Clinician Ratings
 - Instruct and collect CGII-Patient/Caregiver Ratings
 - Administer Columbia Suicide Scale assessed for children 7 years and older
 - Perform follow-up physical and neurological examinations
 - Assess for adverse events
 - Measure vital signs
 - 12-lead ECG
 - EEG
 - Collect bottles from prior visit study medication
 - Adjust dose if necessary
 - Dispense study medication
 - Urine Pregnancy Test for WCBP

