9.5.5.12 Dose Escalation Visit and Unscheduled Visits

- Review background AEDs and other concomitant medications
- Collect and review seizure calendars; provide new calendars
- Administer Columbia Suicide Scale assessed for children 7 years and older
- Perform follow-up physical and neurological examinations
- Assess for adverse events
- Measure vital signs
- Draw blood sample for hematology, chemistry; obtain urine sample from subjects who are toilet trained for urinalysis and pregnancy test for WCBP.
- Collect bottles from prior visit study medication
- Adjust dose if necessary
- Dispense study medication

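### Protocol 9.4.4 allows a further dose increase before the required clinic check of the previous high dose (minor)

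*Protocol*

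**What the plan says.** For children of 30 kg or less, Protocol 9.4.4 starts dosing at 18 mg/kg/day. The dose is then "increased in ~20-50% increments at intervals of not less than 3 days and not more than 2 weeks provided current dose is reasonably tolerated", up to a cap of 63 mg/kg/day. Later adjustments are made "with a minimum of three days between dose changes, unless required for safety". The same section adds a safety visit: "Any and each dose escalation above 54 mg/kg/day requires a clinic visit scheduled 4-6 days after the dose increase". Above 30 kg the visit is triggered at 1500 mg/day and the cap is 1800 mg/day. For the actual steps the reader is told to "see Appendix 4 for suggested dose escalation schedule".

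Appendix 2 footnote 6, copied into SAP Table 1, repeats the visit rule with both thresholds and lets a regular visit count as the dose escalation visit. Section 9.5.5.12 gives the visit's content: examination, vital signs, adverse event review, suicidality scale, and laboratory work ("Draw blood sample for hematology, chemistry; obtain urine sample"). It also lists "Adjust dose if necessary". None of these places says that the next increase must wait for the visit.

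**The concern.** The shortest permitted interval (3 days) is shorter than the earliest permitted visit (day 4). The protocol singles out the top of the dose range for an additional check after every increase, yet its timing rules let the next increase come first. The visit then sees the child on the new dose, and findings at the dose that triggered it are mixed with those at the higher one.

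The top range is where prior pediatric experience is thinnest in the protocol's own account. Section 7 says the four earlier open-label pediatric suspension studies went up to 36 mg/kg/day and that most adverse events were dose-related. At stake is a short unchecked exposure to one further small increase. The efficacy analysis is not affected.

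**Working it through.** **Inputs.** Minimum interval 3 days; visit 4 to 6 days after the increase; thresholds 54 mg/kg/day and 1500 mg/day; caps 63 mg/kg/day and 1800 mg/day (all 9.4.4). Dose steps are from Appendix 4, which gives no day spacing. Day 0 is the first dose.

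**1. Can a second increase above the threshold occur?** With a strict 20% step, no: 54 × 1.2 = 64.8, over 63 mg/kg/day; 1500 × 1.2 = 1800, so any dose above 1500 mg would pass 1800 mg. But 9.4.4 says approximately 20 to 50%, and Appendix 4 prints smaller steps:

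- 30 kg suspension: 1500 → 1650 (+10.0%) → 1800 mg (1800/1650 = +9.1%). Per kg: 1650/30 = 55 and 1800/30 = 60, both above 54.
- Capsules, first dose above 54 mg/kg and second at or below 63 mg/kg:

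| Step | Increase | Lower weight | Upper weight |
|---|---|---|---|
| 1600 → 1800 mg | 12.5% | 1800/63 = 28.57 kg | 1600/54 = 29.63 kg |
| 1575 → 1800 mg | 14.3% | 1800/63 = 28.57 kg | 1575/54 = 29.17 kg |
| 1400 → 1600 mg | 14.3% | 1600/63 = 25.40 kg | 1400/54 = 25.93 kg |

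If footnote 6's 1500 mg threshold also applies at 30 kg or less, the first two bands extend to 30 kg. No other adjacent capsule step gives a band. The 15, 20 and 25 kg suspension tables have one step above the threshold (54 → 63 mg/kg, the cap) and are unaffected. Appendix 4 prints no path for children above 30 kg.

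**2. Timing, 30 kg suspension, 3-day spacing.** 540 mg (day 0), 718 (3), 955 (6), 1270 (9), 1500 (12), 1650 (15), 1800 (18).

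- Visit for 1650 mg: 15 + 4 to 15 + 6 = days 19 to 21.
- Days at 1800 mg before that visit: 19 − 18 = 1 to 21 − 18 = 3.
- Visit for 1800 mg: days 22 to 24, a separate window.

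**3. Stricter reading.** If three full days must lie between changes, spacing is 4 days: 1650 mg on day 20, 1800 mg on day 24, visit on days 24 to 26. The overlap is 0 to 2 days.

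**4. Does a scheduled visit cover it?** Section 9.5.5.3 sets "Visit 3 (end of Week 2 + / 3 days"; Appendix 2 gives ±3 days, so days 11 to 17. At 3-day spacing Visit 3 always precedes 1800 mg and includes examination, vital signs and adverse event review. It meets 1270 mg on day 11, 1500 mg on days 12 to 14, and 1650 mg on days 15 to 17, so 3 of its 7 window days. It cannot serve as the visit due on days 19 to 21. Its procedure list and Appendix 2 show no blood draw, although 9.5.4 says "Blood samples will be drawn at baseline, 2 weeks, 8 weeks, 26 weeks". At 4-day spacing it falls entirely before 1650 mg.

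**The case against.** The strongest reply is that the conflict does not arise under 9.4.4's own step size: no step of 20% from above the threshold fits under the cap. That is correct for a strict 20%. It does not remove the gap, because the figure is approximate and 9.4.4 sends sites to Appendix 4, where the smaller steps are printed as suggestions. It does confine the gap to the paths listed.

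Second, nothing calls the visit a precondition for the next increase. That also stands. The dose-adjustment line in 9.5.5.12 is weak support, since Visits 3 to 6 carry it too. The inference rests mainly on the visit's stated purpose of assessing safety and tolerability.

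Third, the plan already permits larger single jumps to the top dose: 1270 → 1800 mg is +41.7% and 42 → 63 mg/kg is +50%. A hold leaves these untouched, so its protective value is limited. It would still keep the protocol's own check ahead of the next increase on the stepwise paths.

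Fourth, other safeguards exist. Each increase is conditional on reasonable tolerance of the current dose; Appendix 2 footnote 7 allows safety laboratory tests at any visit when warranted; and unscheduled visits are allowed at any time. These depend on judgement and do not require an assessment before the next step.

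**Conclusion.** The concern holds and is minor. As written, a child can go to a higher dose before the protocol's required check of the previous above-threshold dose. On the 30 kg suspension path this means 1 to 3 days (0 to 2 on the stricter reading) at an extra 150 mg. On capsules it concerns steps of 200 to 225 mg at about 28.6 to 30 kg and 25.4 to 25.9 kg.

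The result assumes the shortest permitted intervals and the printed Appendix 4 steps; the extension of the capsule band to 30 kg also assumes footnote 6's 1500 mg threshold. Slower titration reduces or removes the overlap.

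The supplied protocol is the April 2016 text. The SAP refers to Amendment 8.1, whose dosing section is not available here, so a later correction cannot be ruled out. The SAP's copy of footnote 6 still contains no hold.

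**What to change.** Add one sentence to 9.4.4 and to Appendix 2 footnote 6: after any increase to a dose above 54 mg/kg/day or above 1500 mg/day, no further increase is made until the 4 to 6 day dose escalation visit has been completed and reviewed. State whether review requires the laboratory results. If it does, the delay grows by the laboratory turnaround time, which the documents do not give. Using the two-part threshold in both places also removes the small difference between 9.4.4 and the footnote.

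The hold fits the existing rules: days 4 to 6 lie within the 2-week maximum interval, and dose adjustment is already listed at that visit.

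**Cost.** Apart from any wait for laboratory results, the last step is delayed by about 1 to 3 days (0 to 2 on the stricter reading) in a few children. No visit is added on the 30 kg suspension path, where two are already due in separate windows. On capsules footnote 6 already requires the visit. Only a site applying 9.4.4 alone would see one more, at 29.2 to 30 kg on 1575 mg or 29.6 to 30 kg on 1600 mg. The SAP describes main-period treatment in the past tense, so the change mainly serves any later protocol that reuses this dosing text.

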2. SYNOPSIS

Name of Sponsor/Company: Marinus Pharmaceuticals, Inc.

Protocol Number: 1042-0900 Phase of Development: 2a

Title of Protocol: A 26 week Multicenter, Open-Label Proof-of-Concept Trial of Ganaxolone in Children with PCDH19 Female Pediatric Epilepsy And Other Rare Genetic Epilepsies Followed by a 52 Week Open Label Treatment

Primary Objectives: To evaluate the efficacy of open-label ganaxolone as adjunctive therapy for uncontrolled seizures in children with genetic epilepsies. These include, but are not limited to children with protocadherin19 (PCDH19) mutation, cyclin-dependent kinase like 5 (CDKL5) Disorder, Dravet Syndrome and other epileptic syndromes such as idiopathic or genetic types of Lennox-Gastaut syndrome (LGS), Continuous Spike Wave in Sleep (CSWS) and other potential genetic or clinical conditions with or without corresponding genetic condition (referred to as genetic epilepsies) in an open-label proof-of-concept study.

Secondary Objectives: To evaluate the safety and tolerability of open-label ganaxolone as adjunctive therapy for uncontrolled seizures in children with genetic epilepsies.

Study Design and Methodology: After establishing baseline seizure frequency, qualifying subjects will enter the study and be treated with ganaxolone oral suspension or ganaxolone capsules at doses up to 63 mg/kg but not more than 1800 mg/day for up to six months.

Study Population and Main Criteria for Inclusion/Exclusion: Subjects between 2 and 18 years of age with a confirmed PCDH19 mutation, or a confirmed CDKL5 mutation or Dravet syndrome with a confirmed SCN1A mutation or LGS, or CSWS or potential other genetic or clinical conditions with or without corresponding genetic condition and consent of a parent or guardian may be eligible to enter the study.

Seizure criteria as follows:

- a. Have uncontrolled cluster seizures (3 or more seizures over the course of 12 hours) every 6 weeks or less during baseline, or bouts of status epilepticus on intermittent basis, or
- b. Have uncontrolled non-clustered seizures (focal dyscognitive, focal convulsive, atypical absences, hemiclonic seizures, spasms, or tonic-spasm seizures) with a frequency ≥4 seizures per 28-day period during baseline, or
- c. Have ≥4 generalized convulsive (tonic-clonic, tonic, clonic, atonic seizures) per 28-day baseline period during baseline, or

d. Have subclinical CSWS syndrome with or without clinical events on electroencephalogram (EEG).

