- 6. A dose escalation visit is required 4-6 days after escalation to any dose level above 54 mg/kg/day or above 1500 mg/day. A regularly scheduled visit may serve as a dose escalation visit. An unscheduled visit can occur at any time during the 26 week open-label treatment period or the 52 week extension. Samples for concomitant AEDs and study drug levels may also be drawn if warranted in the opinion of the investigator.
- 7. Safety labs can be collected at any visit if warranted in the opinion of the investigator.
- 8. If this is the last study visit, the subject should be instructed on down-titration and scheduled for Visit 11 which is the follow-up visit.

AEs = adverse events; AED = antiepileptic drug; ECG = electrocardiogram; C-SSR=Columbia Suicide Severity Rating; EEG= Electroencephalography; VAS=Visual Analogue Scale

Schedule of Events - 52 Week Open-Label Extension

WEEK	44	62	78	
VISIT	V8	V9	V10 ⁴	V11
	+/- 14	+/- 14	+/- 14	Follow-
	days	days	days	up +/- 7
				days
Screening & Diagnosis				,
Background AEDs Review	X	X	X	X
Concomitant Med Review	X	X	X	X
Safety Assessments				
Vital Signs ⁵	X	X	X	X
Physical Examination	X	X	X	
Neurological Examination	X	X	X	
Safety Labs (Blood ⁷ and Urine ²)	X	X	X	
Urine Pregnancy Test (WCBP)	X	X	X	
Administer C-SSRS	X	X	X	X
Review safety and record AEs	X	X	X	X
Efficacy Assessments				
Instruct/ Provide Seizure Calendar	X	X	X	
Subject Calendar Review	X	X	X	X
EEG	X	X	X	
Complete CGII-C	X	X	X	
Instruct and Collect CGII-P	X	X	X	
Other Assessments				
VAS		X	X	
PK/PD Assessments				
Concomitant AED medications	X	X	X	
Study Drug Blood Samples	X	X	X	
Neurosteroid levels	X	X	X	
Study Medication				
Dispense Medication	X ³	X ³	X ³	

Collect bottles from prior visit study medication	X	X	X	X
Instruct on Down-titration			X8	

- 1. Physical and neurological exam records performed at the same center within 60 days of screening visit may be used in place of screening exam. Visits 3, 4, 5 and 6 may be follow-up exams. Tanner Scores will be collected.
- 2. Obtain urine sample for those who are toilet trained.
- 3. Adjust dose if necessary.
- 4. This visit could also be an Early Termination visit. At this visit, investigator confirms if the subject qualifies for the 52 week extension, subjects must have completed all scheduled clinical study visits and have shown a minimum 35% improvement in mean seizure frequency per 28 days vs. baseline.
- 5. Vital signs including temperature, blood pressure, pulse, height and weight.

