1.3 SUMMARY OF THE STUDY DESIGN

1.3.1 General Study Design and Plan

The purpose of this proof-of-concept study is to evaluate GNX as adjunctive therapy for uncontrolled seizures in female children with PCDH19 mutations, CDKL5 mutation and SCN1A mutation (Dravet syndrome), and other epileptic syndromes such as LGS and CSWS in an open-label proof-of-concept study. After establishing baseline seizure frequency, qualifying subjects entered the main portion of the study and were treated with open-label GNX oral suspension or GNX capsules at doses up to a maximum of 1800 mg/day (63 mg/kg/day for those dosed on a mg/kg basis) for up to 6 months. Maximum study participation will be 94 weeks: a screening period to establish baseline seizure frequency, up to 26 weeks treatment, and a 52-week open-label extension (OLE) for patients who benefit from GNX treatment and up to 4 weeks down-titration. Patients who continue to benefit from GNX treatment during the 52-week OLE will be permitted to continue to receive GNX.

Approximately 10 subjects with PCDH19, 10 subjects with CDKL5 Disorder, 10 subjects with Dravet Syndrome, and up to 10 subjects with LGS, and up to 10 subjects with CSWS, were originally planned to participate. But, no subjects with Dravet Syndrome were recruited for enrollment and only 2 subjects with CSWS actually participated.

After signing the informed consent form, subjects or their legally authorized representatives were asked to chart seizures in a subject seizure calendar in order to establish baseline frequency for up to 12 weeks. After establishing baseline seizure frequency, eligible subjects entered the study and were treated with open-label GNX oral suspension or GNX capsules.

The Schedule of Events for 26-week treatment period is presented in [Table 1](#). The Schedule of Version: 2.0

Table 2.

Table 1: Schedule of Events – 26 Week Treatment Period

Week		0	2	4	8	17	26	
Visit	V1 Screening	V2 Baseline	V3 ± 3 days	V4 ± 3 days	V5 ± 3 days	V6 ± 7 days	V7 Final Visit ⁴ ± 7 days	Unscheduled Visit or Dose Escalation Visit ⁶
Screening & Diagnosis								
Informed consent	X							
Demographics	X							
Medical History	X	X						
Retrospective Seizure Diary Collection and Review	X							
Inclusion/Exclusion criteria	X	X						
Background AEDs Review	X	X	X	X	X	X	X	X
Concomitant Med Review	X	X	X	X	X	X	X	X
Safety Assessments								
ECG	X			X				
Vital Signs ⁵	X	X	X	X	X	X	X	X
Physical Examination ¹	X	X	X	X	X	X	X	X

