7. SAFETY ANALYSIS

All safety analyses will be performed by cohort and overall in the Safety Population. The highest percentage of the maximum allowable daily dose that subjects received will be summarized with descriptive statistics. The cumulative dosage that subjects received will be summarized with descriptive statistics, separately for subjects receiving their dosage on a mg/kg basis and those receiving it on a mg basis. For subjects who received dosing on a mg/kg basis at the start of the study and then switched to a mg basis, the doses with a mg basis will be converted to a mg/kg basis by dividing the mg by the subjects' most recent weight prior to the mg basis. A subject data listing will be provided with full details of the study drug dispensation.

Safety assessments include:

- AEs
- Clinical laboratory tests
- Vital signs including temperature, blood pressure, pulse rate, and weight
- Neurological and physical examinations
- 12-lead ECG
- EEG
- C-SSRS

Baseline is defined as the last non-missing value obtained before the first treatment. Assessments performed at multiple post-baseline time points will be summarized at each time point for which they are scheduled. The listings will include any assessments performed at unscheduled time points.

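### For children of 30 kg or less, protocol 9.4.4 states the maximum dose in mg/kg only, which contradicts the 1800 mg/day ceiling elsewhere for weights above 28.57 kg; the extra-visit trigger has a similar, narrower mismatch

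*Protocol*

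**What the plan says.** **Maximum dose.** Protocol 9.4.4 treats two weight groups separately. Above 30 kg: "The maximum allowable dose is 1800 mg/day". The paragraph for the lighter group opens "For children weighing 30 kg (66 lbs) or less, dosing should start at 18 mg/kg/day" and ends "The maximum allowable dose is 63 mg/kg/day", followed by a pointer to the suggested schedules in Appendix 4. It contains no mg/day limit.

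The Synopsis applies both limits to everyone: "at doses up to 63 mg/kg but not more than 1800 mg/day for up to six months". It repeats the pair under the test product. Section 9.1 gives 1800 mg/day with no weight split. In Appendix 4 the 15, 20 and 25 kg suspension tables end at 63 mg/kg, but the 30 kg table ends at 60 mg/kg, which is 1800 mg.

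**Extra safety visit.** For the lighter group 9.4.4 says "Any and each dose escalation above 54 mg/kg/day requires a clinic visit scheduled 4-6 days after the dose increase". The 1500 mg/day trigger appears in 9.4.4 only for subjects above 30 kg. Appendix 2 note 6 says "A dose escalation visit is required 4-6 days after escalation to any dose level above 54 mg/kg/day or above 1500 mg/day", without reference to weight group. The SAP's schedule of events repeats that note.

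**SAP.** Section 1.3.1 describes treatment "at doses up to a maximum of 1800 mg/day (63 mg/kg/day for those dosed on a mg/kg basis". Section 7 says "The highest percentage of the maximum allowable daily dose that subjects received will be summarized with descriptive statistics" and does not define that maximum.

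**The concern.** A maximum dose and a safety-visit rule in children should each have one value for a given child. Near the top of the lighter weight band they do not. A site that works from 9.4.4, the operative dosing section, can go above the ceiling in the Synopsis and 9.1. It can also leave out a visit that note 6, taken at its word, requires.

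Section 9.4.4 is also uneven when read alone. A child of exactly 30 kg may reach 63 × 30 = 1890 mg/day, while a child just over 30 kg is limited to 1800 mg/day. Escalation to 1600 mg/day calls for a visit just above 30 kg, where 1500 mg is the trigger. It calls for none at 30 kg, where 1600/30 = 53.3 mg/kg is below 54.

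The analysis is touched only lightly: the percentage of maximum dose in SAP 7 inherits whichever limit is programmed.

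**Working it through.** **Inputs.** 63 and 54 mg/kg/day (9.4.4, 30 kg or less); 1800 mg/day (Synopsis, 9.1); 1500 mg/day (Appendix 2 note 6); dose steps from Appendix 4.

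**Formulas.** Dose in mg/day = mg/kg/day × weight. Crossover weight = mg/day limit ÷ mg/kg/day limit.

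**1. Reproduce Appendix 4.** Top steps at 63 mg/kg: 15 × 63 = 945, 20 × 63 = 1260 and 25 × 63 = 1575 mg, as tabulated and all below 1800. At 30 kg: 50 × 30 = 1500, 55 × 30 = 1650 and 60 × 30 = 1800 mg, also as tabulated. A 63 mg/kg step at 30 kg would be 1890 mg; the table has none.

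**2. Maximum.** Crossover: 1800/63 = 28.57 kg. At or below this weight the mg/kg limit is the tighter one and nothing conflicts.

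| Weight (kg) | 63 mg/kg (mg/day) | Excess over 1800 mg/day |
|---|---|---|
| 29 | 1827 | 27 (1.5%) |
| 29.5 | 1858.5 | 58.5 (3.2%) |
| 30 | 1890 | 90 (5.0%) |

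**3. Visit trigger, note 6 read literally.** Crossover: 1500/54 = 27.78 kg. Above that weight, a dose over 1500 mg but not over 54 mg/kg × weight needs a visit under note 6 and none under 9.4.4.

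| Weight (kg) | Range in dispute (mg/day) |
|---|---|
| 28 | above 1500, up to 1512 |
| 29 | above 1500, up to 1566 |
| 30 | above 1500, up to 1620 |

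**4. Do listed doses fall in that range?** Some capsule steps do. The 1575 mg step is at or below 54 mg/kg from 1575/54 = 29.17 kg (52.5 mg/kg at 30 kg). The 1600 mg step is so from 1600/54 = 29.63 kg (53.3 mg/kg at 30 kg). The 30 kg suspension steps do not: 1500 mg (50 mg/kg) meets neither trigger, and 1650 mg (55 mg/kg) meets both.

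**5. Percentage of maximum in SAP 7, at 30 kg.** A dose of 1800 mg/day scores 1800/1890 = 95.2% on the 63 mg/kg limit and 1800/1800 = 100% on the mg limit. A dose of 1890 mg/day scores 100% or 1890/1800 = 105%. The gap is at most about 5 points and exists only above 28.57 kg, up to 30 kg.

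**The case against.** The best defence on the maximum is that 9.4.4 is an incomplete restatement. The Synopsis gives the joint limit twice, 9.1 gives 1800 mg/day, and the Per Protocol definition in 9.7.1 takes 1800 mg/day as its upper bound. The sentence in question is followed by a pointer to Appendix 4, whose 30 kg table stops at 1800 mg. No passage writes or tabulates 1890 mg/day. This limits how serious the point is but does not remove it. The Appendix 4 schedules are only suggested, so they do not override a stated maximum, and a site reading 9.4.4 alone sees no mg/day limit for this group.

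On the trigger, note 6 can be read as a compressed form of 9.4.4, since its two thresholds are exactly those of the two weight groups. On that reading there is no conflict. That stands as a possibility, but the note does not say so. The conflict over the maximum is unaffected either way.

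On the SAP, section 1.3.1 already assigns a maximum by dosing basis, so a programmer has something to work from. This stands, and it reduces the SAP element to a consequential remark.

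Finally, the SAP cites protocol Amendment 8.1 (August 2017), while the protocol supplied is the April 2016 version. The two do differ elsewhere: SAP 11 describes response thresholds in protocol 9.5.2 that the supplied 9.5.2 lacks. A later 9.4.4 may already be corrected; this cannot be checked here.

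**Conclusion.** The contradiction over the maximum is in the text: 63 mg/kg/day alone in 9.4.4 against 1800 mg/day for all subjects in the Synopsis and 9.1. It affects weights above 28.57 kg up to and including 30 kg, and is at most 90 mg/day (5%). The trigger mismatch starts above 27.78 kg and depends on a literal reading of the 'or' in note 6.

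A reader might infer three stronger things that the documents do not support:

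- That the plan intends doses of 1890 mg/day. That figure comes only from applying one sentence of 9.4.4 at 30 kg.
- That every dose from 1500 to 1620 mg/day in children of 27.8 to 30 kg is in dispute. The range narrows with weight and reaches 1620 mg only at 30 kg.
- That the exposure analysis is materially compromised. The effect is at most about 5 points, in one descriptive summary, for children in a band of about 1.4 kg (30 − 28.57).

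The point is worth correcting because it concerns a paediatric dose limit and a safety visit. No view is taken here on which limit is right. All of this rests on the protocol version supplied.

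**What to change.** First check 9.4.4 in Amendment 8.1. If the wording is unchanged:

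1. Make the maximum read identically in 9.4.4 (30 kg or less), the Synopsis, 9.1 and Appendix 4, stating how the mg/kg and mg/day limits combine for this group. The sponsor decides which limit governs.
2. Do the same for the visit trigger in 9.4.4 and Appendix 2 note 6, and in the SAP's copy of that note. If the note was meant to follow the two weight groups, it should say so.
3. Align SAP 1.3.1 with the reconciled limit, and define the maximum allowable daily dose in SAP 7 as that limit at each subject's weight.

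The cost is wording in the protocol and SAP. Depending on the sponsor's decision, it may also mean a few more or fewer visits for children of about 28 to 30 kg.
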